7.8 Efficacy Analysis

The primary objective of the study is to determine the effectiveness of treatment with vortioxetine on subject goal achievement after changing antidepressant medication for treatment of MDD. The primary endpoint is the proportion of subjects who changed to treatment with vortioxetine and achieved their individually identified goals as demonstrated by an outcome GAS Score of ≥ 50 at Week 12. This proportion will be summarized at Week 12. All efficacy analyses will use the FAS.

7.8.1 Primary Efficacy Endpoint

The GAS is a tool to measure the progress each subject has towards achieving their individualized goals. While the outcome measure is unique to each subject, standardized scoring is applied to allow for statistical analysis.

The GAS allows for 1 of 2 types of goals to be set:

- (1) Subject defined goals allow a “subject’s chief complaint” approach taken towards establishing the goal, with no specific limitations set for the type or focus of the goal, beyond requiring that it meets the basic standards of measurability, equidistance, and difficulty.
- (2) Domain-defined goals are more structured in nature, presenting the subject with an array of broadly defined domains and more specific subdomains. After selecting an appropriate domain and (where applicable) subdomain, the clinician will work with the subject to establish a specific goal that fits within the selected category.

For GAS, a total of 3 goals will be selected, 1 subject defined and 2 from pre-defined domain categories. A 5-point rating scale will then be applied to each of the 3 goals. A semi-structured interview will be conducted with each subject to conduct goal-setting at the outset of the study.

Another evaluation will take place at Week 6 and Week 12/End of Study visits or at Early Termination Visit (as applicable) to determine the level of progress at that time, with assignment of appropriate scores. It takes subjects approximately 45 minutes to complete the GAS.

Calculating the Overall GAS

The goals identified are incorporated into the single GAS score by applying a formula:

$$\text{Overall GAS} = 50 + \frac{10 * \sum(w_i x_i)}{\sqrt{(1-\rho) \sum w_i^2 + \rho(\sum w_i)^2}}$$

Where:

w_i = the weight assigned to the i th goal (if equal weights, $w_i = 1$)

x_i = the numerical value achieved (between -2 and +2)

ρ = the expected correlation of the goal scales

(For practical purposes, most commonly approximates to $\rho=0.3$)

For this study, a choice of weight is based on importance of the goal. Weight is 1, 2, and 3 for least important, moderately important and most important goals, respectively. The expected correlation of 0.3 was selected for this study.

The GAS will be summarized for both Week 6 and Week 12 using both percents of response and as a continuous score. An overall GAS score greater than 50 is considered as a response.

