5.2 Endpoints

5.2.1 Primary Endpoint

The primary endpoint is to estimate the proportion of subjects who achieve their identified goals as demonstrated by an outcome Goal Attainment Scale (GAS) Score of \geq 50 at Week 12.

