5.1 Primary Endpoint

The primary endpoint is to estimate the proportion of subjects who achieve their identified goals as demonstrated by an outcome Goal Attainment Scale (GAS) Score of ≥ 50 at Week 12.

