6.0 DETERMINATION OF SAMPLE SIZE

As no formal hypothesis testing is performed for the primary endpoint, the purpose of sample size estimation is to determine the adequate sample size needed to provide a precise estimate for the response rate (GAS Score ≥ 50) with 95% CIs.

Conservatively estimating that 50% of subjects will be responders (GAS ≥ 50) and that 100 subjects will complete the study, CIs will be ± 0.098 around the point estimate (proportion of responders).

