7.10 Interim Analysis

The responder rate based on GAS score ≥ 50 will be calculated. The conditional probability of a responder rate of less than 50% at 120 subjects will be assessed; that is, using the data /trend of 60 patients at the interim look, the probability of (responder rate $< 50\%$) at the end of study (i.e., 120 subjects) will be calculated.

In addition, the change in PHQ9 and PDQ will be evaluated for internal decision making.

The report to be prepared for the interim analysis should include the tables for the following: demographics, disposition, GAS Response percents, GAS change from baseline, PHQ-9, and PDQ-D.

The end of the study will be the date of the last safety follow-up visit of the last subject based either on the first 60 completed subjects or the final 120 completed subjects.

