7.11 Changes in the Statistical Analysis Plan

To be identified.

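### SAP 7.8.1 counts a GAS response only above 50, while SAP 5.1, 6.0, 7.8 and 7.10 and Protocol 5.2.1, 13.1.3 and 13.3 count 50 or above

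*SAP*

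**What the plan says.** SAP 7.8.1 (Primary Efficacy Endpoint) gives the formula for the overall GAS score, the goal weights and the assumed correlation, and ends with the rule "An overall GAS score greater than 50 is considered as a response". The sentence just before it applies response percentages to two visits: "The GAS will be summarized for both Week 6 and Week 12 using both percents of response and as a continuous score".

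Elsewhere the threshold includes 50:

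- SAP 5.1, primary endpoint: "outcome Goal Attainment Scale (GAS) Score of ≥ 50 at Week 12".
- SAP 7.8, the parent section of 7.8.1: "individually identified goals as demonstrated by an outcome GAS Score of ≥ 50 at Week 12".
- SAP 6.0, sample size: "Conservatively estimating that 50% of subjects will be responders (GAS ≥ 50".
- SAP 7.10, interim analysis: "The responder rate based on GAS score ≥ 50 will be calculated".
- Protocol 5.2.1, 13.1.3 and 13.3 use ≥50 for the primary endpoint, its analysis and the sample size.

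Neither document says which rule prevails. SAP 7.11, on changes to the plan, contains only "To be identified".

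The protocol synopsis (Section 2.0) is split in the text available. Its primary endpoint line prints a strict sign, while its statistical and sample-size paragraphs print ≥50. The strict sign there may be a symbol lost in reading the PDF, so nothing below relies on it. The SAP 7.8.1 rule is spelled out in words and cannot be explained that way.

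**The concern.** The two rules differ for every subject who scores exactly 50, and this is the cut-off of the only primary estimate. SAP 7.8.1 is where a programmer would look to derive the variable: it carries the primary endpoint heading and is the only section with both the score derivation and a response rule. Protocol 13.1 also assigns the SAP the detailed definition of analysis variables. For the Week 6 response percentages, 7.8.1 is the only stated rule, since the endpoint statements using ≥50 refer to Week 12.

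If 7.8.1 is programmed as written, the reported Week 12 rate will be lower than under the stated primary endpoint. It will also rest on a different definition from the interim projection, which uses ≥50 and asks how likely the final rate is to fall below 50%. The trial is open-label and single-arm, and GAS response percentages are reported at the interim, so either rule could be defended from the SAP after data have been seen.

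**Working it through.** **Planned precision.** Inputs from SAP 6.0 and Protocol 13.3: p = 0.50, n = 100 completers, 95% CI. Half-width = 1.96 × √(0.25/100) = 0.098, which matches the stated ±0.098. It depends only on p and n, so the choice of threshold does not change it.

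**Possible scores.** Inputs from SAP 7.8.1: three goals, ratings x from -2 to +2, weights w = 1, 2, 3, ρ = 0.3.

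- Σw² = 1 + 4 + 9 = 14 and (Σw)² = 36.
- Denominator = √(0.7 × 14 + 0.3 × 36) = √20.6 = 4.539.
- One unit of Σwx is worth 10/4.539 = 2.203 points.
- Σwx takes every integer from -12 to +12, so there are 25 possible scores, from 23.6 to 76.4.
- The next score above 50 is 52.2, so the strict rule in practice means at least 52.2.

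**Patterns at exactly 50.** A score of 50 requires x₁ + 2x₂ + 3x₃ = 0. Of 5³ = 125 patterns, nine satisfy this: (0,0,0), (-2,-2,2), (-2,1,0), (-1,-1,1), (-1,2,-1), (1,-2,1), (1,1,-1), (2,-1,0) and (2,2,-2). By symmetry (125 − 9)/2 = 58 patterns score above 50, and 58 + 9 = 67 score 50 or above. These are counts of patterns, not probabilities.

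**Effect on the responder rate.** If a share q of subjects scores exactly 50, the strict rule lowers the rate by q. With q = 0.05 that is 5 points, or 3 of 60 subjects at the interim. With q = 0.10 it is 10 points, or 6 of 60.

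The documents give no distribution of ratings, so q has to be assumed. The assumption here is trivariate normal ratings rounded to the five-point scale, with a common mean set to give the chosen ≥50 rate, correlation 0, 0.3 or 0.6, and SD 0.8, 1.0 or 1.2 (1,000,000 draws):

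| Rate under ≥50 | Rate under >50, range | Fall, points | Middle case (correlation 0.3, SD 1) |
|---|---|---|---|
| 50% | 34.7% to 42.9% | 7 to 15 | 40.9% |
| 65% | 49.6% to 58.2% | 7 to 15 | 56.1% |
| 80% | 67.3% to 74.7% | 5 to 13 | 72.9% |

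In the middle case at 50%, the fall is 50 − 40.9 = 9.1 points: 6.2 from subjects with all goals at 0 and 2.9 from the eight mixed patterns. A second calculation held correlation at 0.3 and SD at 1 and varied the mean goal rating from -1 to +0.5. It puts about 4% to 9% of subjects at exactly 50; at mean 0 the two rates are 54.6% and 45.3%.

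**The case against.** The text leans heavily towards ≥50. Every formal endpoint definition in the SAP and the protocol body uses it, and SAP 7.8 states it just before 7.8.1. The strict sentence closes a scoring description and may simply be loose wording. Any harm is conditional on someone programming that sentence. The primary endpoint carries no hypothesis test, the precision figure is unaffected, and the fix is a single phrase, so it could be rated a minor correction.

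The size is also model-dependent. The 15-point end at a 50% rate needs correlation 0.6 with SD 0.8; with SD 1.2 the fall there is about 7 to 9 points. The pattern counts assume each weight is used once, which is the natural reading of SAP 7.8.1 although ties are not expressly barred. With three equal weights, 19 patterns rather than nine would score exactly 50. Finally, SAP 7.11 is an unfilled placeholder, so its silence says little.

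Most of this stands as a limit on the claim. The intent is probably ≥50, which is why the correction goes in that direction. The size is an assumption, and SAP 7.11 is weak evidence. It does not remove the contradiction: no text reconciles the two rules, and the outlying one sits where the variable is derived.

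**Conclusion.** The plan is wrong as written: it contains two response rules for its sole primary estimate. The strict rule lowers the responder rate by exactly the share of subjects scoring 50, a share the documents do not allow anyone to know in advance. Under the rounded-normal assumptions, that share is about 7 to 15 points when the ≥50 rate is 50% or 65%, and 5 to 13 points when it is 80%. For scale, the planned half-width is 9.8 points, so the ambiguity can be about as large as the sampling uncertainty the study was sized to control. No pass/fail conclusion changes. What changes is the reported rate and its consistency with the interim. Because it concerns the primary threshold, it must be settled before programming is finalised.

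**What to change.** In SAP 7.8.1, replace the strict wording with greater than or equal to 50, so that it agrees with SAP 5.1, 6.0, 7.8 and 7.10 and Protocol 5.2.1, 13.1.3 and 13.3. The same rule then covers the Week 6 and Week 12 response percentages and the interim. Check the primary endpoint line in the protocol synopsis against the source file, and correct it if it really prints a strict sign. The cost is one phrase and one check, with no change to design, data collection or sample size.

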7.8.2 Secondary Efficacy Endpoint(s)

7.8.2.1 PHQ-9

The PHQ-9 will be used as a secondary efficacy measure of depression severity. This is a well-established patient reported outcome tool for assessment of change in depressive symptoms and is a sensitive measure of depression severity.

The PHQ-9 consists of a 9-item scale originally developed for primary care settings, with 1 item corresponding to each of the 9 MDE symptom criteria for depression in DSM, asking if they have bothered the patient over the last 2 weeks. Each question is rated on a scale from 0 (not at all) to 3 (nearly every day). If any problems are answered 1 or higher, a final question on how difficult those problems made it to do work, take care of things at home, or get along with other people is completed rated from not difficult at all to extremely difficult. The 9 questions are summed to a total score ranging from 0 to 27 with higher scores reflecting greater severity. It

takes approximately 5 minutes to complete the PHQ-9. The total score for the PHQ-9 is analyzed as a continuous variable.

7.8.2.2 *PDQ-D*

The PDQ-D, a validated version of the original PDQ specifically modified to depressed patients, will be used to evaluate self-reported cognitive complaints in patients with MDD. The PDQ was originally developed to assess cognitive complaints in patients with multiple sclerosis. However, it does address cognitive aspects highly relevant for depression, including attention and concentration, retrospective memory, prospective memory, and planning and organization. It takes approximately 10 minutes to complete the PDQ-D. The score from the PDQ-D is analyzed as a continuous variable.

7.8.2.3 *Clinical Global Impression Scales*

The CGI was developed to provide global measures of the severity of a patient's clinical condition during clinical studies. The CGI scales consist of 2 subscales: the CGI-S and the CGI-I. CGI-S and CGI-I raters will be required to have suitable experience and training (as deemed by sponsor) to be eligible to rate subjects within the study. The total time to score the CGI is approximately 1 to 2 minutes after the clinical interview.

CGI-S

The CGI-S is a clinician rated scale designed to assess global severity of illness and change in the clinical condition over time. The CGI-S provides the clinician's impression of the patient's current state of mental illness. The clinician uses his or her clinical experience of this patient population to rate the severity of the patient's current mental illness on a 7-point scale ranging from 1 (normal - not at all ill) to 7 (among the most extremely ill patients). The CGI-S is analyzed as a continuous variable.

CGI-I

The CGI-I assesses the subject's improvement (or worsening). The clinician is required to assess the subject's condition relative to Baseline (Randomization/Day 1) on a 7-point scale ranging from 1 (much improved) to 7 (much worsened). In all cases, the assessment should be made independent of whether the rater believes the improvement/worsening is drug-related or not. The CGI-I is analyzed as a continuous variable.

7.8.2.4 *Q-LES-Q*

The Q-LES-Q is a scale designed to allow researchers to assess the degree of a subject's quality of life in various areas of daily living. Ninety-one of the 93 items are assembled into 8 categories: physical health/activities, feelings, work, household duties, school/course work, leisure time activities, social relations, and general activities. The items are grouped according to these categories and the items are each scored on a 5-point scale, from 1 (not at all or never) to 5 (frequently or all the time), to indicate the degree of enjoyment or satisfaction experienced.

Higher scores indicate greater enjoyment/satisfaction. Typically a self-report measure, this scale will be read to the subject by a member of the site staff and verbatim answers recorded to ensure all data points are captured. It takes approximately 40 to 45 minutes to complete the Q-LES-Q. Each of the 8 sub-scores from the Q-LES-Q is analyzed as a continuous variable.

7.8.2.5 WHO-5

The WHO-5 is a short, self-administered questionnaire covering 5 positively worded items, related to positive mood (good spirits, relaxation), vitality (being active and waking up fresh and rested), and general interests (being interested in things). Administering the WHO-5 takes 2 to 3 minutes to complete. The raw score is calculated by totaling the figures of the five answers. The raw score ranges from 0 to 25, 0 representing worst possible and 25 representing best possible quality of life. To obtain a percentage score ranging from 0 to 100, the raw score is multiplied by 4. A percentage score of 0 represents worst possible, whereas a score of 100 represents best possible quality of life.

[figure not shown]
7.8.3 Additional Efficacy Endpoint(s)

7.8.3.1 Company Confidential Information

7.8.3.2 Company Confidential Information

[figure not shown]
7.8.3.3 Company Confidential Information

Company Confidential Information

7.8.3.4 Company Confidential

[figure not shown]
Company Confidential Information

7.8.4 Analyses for Secondary and Additional Endpoints

For the secondary endpoints of outcome measures of GAS Score, PHQ-9, PDQ-D, Q-LES-Q Score, WHO-5, and CGI-S, total scores and changes from Baseline will be summarized by each time point of Baseline, Week 6 (as appropriate) and by each time point of Baseline and Week 12. These changes from Baseline will be analyzed using paired t-tests. Also, for each of the outcome measurements, change from Baseline at Week 12 will be analyzed using paired t-tests. Tests of significance will be 2-tailed with alpha level at 0.05. CGI-I Scores will be summarized at Week 12 using descriptive statistics.

Company Confidential Information

Additionally, data will be summarized by the following response and remission rates, respectively:

- response defined on the PHQ-9 ($\geq 50\%$ reduction in total score from Baseline) at week 6 and week 12
- response based on CGI-I (CGI-I score of ≤ 2) at week 6 and week 12
- remission defined on PHQ-9 (PHQ-9 score of ≤ 4) at week 6 and week 12
- remission based on CCI-S (CGI-S score of ≤ 2) at week 6 and week 12.

Company Confidential Information

In order to assess Goal Attainment Scaling as a sensitive, reliable measure of response to drug treatment for depression, a series of analyses will be performed to examine the GAS approach against other measures assessed in the study, as well as to evaluate change in GAS scores over time. A full description of the analysis will be described in a separate validation plan.

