7.5 Procedures for Discontinuation or Withdrawal of a Subject

The investigator may discontinue a subject's study participation at any time during the study when the subject meets the study termination criteria described in Section 7.4. In addition, a subject may discontinue his or her participation without giving a reason at any time during the study. Should a subject's participation be discontinued, the primary criterion for termination must be recorded by the investigator. In addition, efforts should be made to perform all procedures scheduled for the Early Termination Visit. Discontinued or withdrawn subjects will not be replaced.

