4.4 Study Design

This study is an open-label, single-arm, multicenter, prospective, phase 4, interventional, flexible dose study (as per the Trintellix US package insert) to determine the effectiveness of treatment with vortioxetine on subject goal achievement after a change in antidepressant medication for the treatment of MDD.

This study is comprised of a 3-week Screening Period (maximum 21 days), to be followed by a 12-week Treatment Period and a 4-week Safety Follow-up Period. Study visits will occur at Baseline (Day 1), and Weeks 2, 4 (Telephone), 6, 9 (Telephone), and 12. This study will enroll approximately 120 subjects and will be conducted at approximately 25 sites in the United States.

This study will enroll men and women between the ages of 18 and 65, inclusive, with a primary diagnosis of MDD, who have previously been treated within 6 weeks of Screening or are currently being treated for a major depressive episode (MDE) with an approved antidepressant for 6 weeks or longer at an adequate dose. Subjects who are dissatisfied with their current or recent antidepressant and are interested in a change in antidepressant treatment will be eligible for Screening.

The change in antidepressant medication will be based on the investigator's judgment in collaboration with the subject's level of dissatisfaction with their current or recent antidepressant treatment (ie, residual mood symptoms, intolerable side effects). Subjects also need to be eligible

per the Trintellix US package insert and sign and date a written, informed consent form and any required privacy authorization prior to the initiation of any study procedures.

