7.2 Analysis Sets

In this study, 3 kinds of analysis sets are defined: full analysis set (FAS), per protocol set (PPS) and safety analysis set.

The FAS, used for primary effectiveness analysis, will include all subjects who were enrolled in the treatment period and received at least 1 dose of the study drug and completed at least 1 GAS assessment post-Baseline. In FAS effectiveness summaries, subjects will be considered as vortioxetine-treated no matter what dose levels were received during the study.

A PPS will include all FAS subjects who had no major protocol violations. Subjects to be excluded from the PPS, whether due to protocol violations or noncompliance to the dosing prescribed by the treating physician, will be identified in the minutes of the subject evaluability assessment.

The Safety Analysis Set will include all subjects who were enrolled and received at least 1 dose of study medication. In safety summaries, all subjects will be analyzed as vortioxetine-treated.

The sponsor will verify the validity of the definitions of the analysis sets as well as the rules for handling data, with consulting a medical expert as needed. If necessary, the Handling Rules for Analysis Data will be supplemented with new handling rules that were not discussed at the planning stage. The Handling Rules for Analysis Data must be finalized prior to database lock.

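### The Week 12 paired t-tests leave out FAS subjects with no Week 12-window value and do not use their Week 6 score; a repeated-measures analysis is a cheap improvement

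*SAP*

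**What the plan says.** SAP 7.8.4 covers GAS score, PHQ-9, PDQ-D, Q-LES-Q, WHO-5 and CGI-S. After describing summaries at Baseline, Week 6 where it applies, and Week 12, it states: "These changes from Baseline will be analyzed using paired t-tests". It adds that "for each of the outcome measurements, change from Baseline at Week 12 will be analyzed using paired t-tests" and that "Tests of significance will be 2-tailed with alpha level at 0.05". Protocol 13.1.3 says the same. The Study Summary (Protocol 2.0) also names paired t-tests.

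SAP 7.8 places all efficacy analyses on the FAS. SAP 7.2 admits a dosed subject who "completed at least 1 GAS assessment post-Baseline", so a Week 6 GAS alone is enough. SAP 7.1 tabulates non-missing values. Neither document shows an imputation rule, a longitudinal model or a missing-data sensitivity analysis for these scales.

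Three other provisions bear on the point:
- Protocol Appendix A schedules GAS, PHQ-9, PDQ-D, WHO-5 and CGI-S at Baseline, Week 6 and Week 12 (CGI-S also at Week 2). Q-LES-Q is scheduled at Baseline and Week 12 only.
- Protocol 9.3.5 asks for the full set of final assessments around the time a subject stops study drug early.
- SAP 7.1.2 sets visit windows that meet midway between consecutive visits and keeps the value nearest the scheduled day.

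On numbers, SAP 4.4 says: "This study will enroll approximately 120 subjects and will be conducted at approximately 25 sites in the United States". SAP 6.0 counts on 100 completers, and Protocol 7.5 says: "Discontinued or withdrawn subjects will not be replaced".

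**The concern.** The Week 12 result carries the FAS label but describes only FAS subjects who have a value in the Week 12 window. For a subject who leaves after Week 6, a score on the same scale is already in hand, yet it plays no part in the Week 12 estimate.

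This matters more in a single-arm trial. There is no control group in which the effect of selective dropout could partly cancel, and the mean change is itself the finding. SAP 5.0 also looks to these validated scales to support a primary measure that is a new adaptation. Selective loss is plausible, because lack of effectiveness is one of the withdrawal categories in Protocol 7.4. The risk is an overstated mean improvement and an interval that covers less often than its nominal 95%.

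**Working it through.** **1. The plan's own figure.** 1.96 × √(0.5 × 0.5 / 100) = 0.098, as SAP 6.0 states. Implied non-completion is (120 − 100) / 120 = 16.7%. The documents give no SD, effect size or power for the secondary scales, so the values below are assumptions.

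**2. Which early leavers are lost at Week 12.** Week 6 is Day 43 and Week 12 is Day 85, so the Week 12 window opens at (43 + 85) / 2 = Day 64. If the Week 9 call (Day 64) counts as a visit, it opens at (64 + 85) / 2 = Day 74.5. An earlier Early Termination value is not a Week 12 value, and it can also lose to the scheduled Week 6 value under the nearest-day rule.

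**3. A bound.** Suppose the poorest sixth at Week 6 all leave, changes are normal, and r is the correlation between Week 6 and Week 12 change. The bias in SDs of change is r × φ(z) / (1 − d), with d = 1/6 and z = −0.967. That is r × 0.250 / 0.833 = 0.30r, or 0.12, 0.18 and 0.24 SD for r = 0.4, 0.6 and 0.8. With an assumed SD of 6 these are 0.72, 1.08 and 1.44 points.

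**4. Simulation.** 120 subjects and 2000 trials per setting. Assumed: true Week 12 change −7, SD of change 6, correlation of Baseline with change −0.4, dropout 16.7% after Week 6 depending on the Week 6 change, and no in-window Early Termination values. Overstatement by the Week 12 paired t-test, in points:

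| Log-odds of leaving per SD poorer response | r = 0.4 | r = 0.6 | r = 0.8 |
|---|---|---|---|
| 0.5 | 0.17 | 0.28 | 0.42 |
| 1.0 | 0.35 | 0.53 | 0.72 |
| 2.0 | 0.56 | 0.79 | 1.07 |

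The comparator is the maximum-likelihood estimate, obtained by regressing Week 12 on Baseline and Week 6 in completers and averaging over all subjects. It stays within 0.04 of the truth in every cell. Standard errors of the t-test estimate are 0.56 to 0.62, and those of the comparator are similar.

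**5. Effect on intervals and tests.** Coverage is Φ(1.96 − b) − Φ(−1.96 − b), with b = bias / SE.
- Low end: 0.17 / 0.59 = 0.29, coverage about 94%.
- Middle: 0.53 / 0.58 = 0.91, coverage about 85%.
- High end: 1.07 / 0.56 = 1.91, coverage about 52%.

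The test statistic for the true change is about 7 / 0.6 ≈ 12, so no test outcome changes.

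**6. Varying the assumptions** (r = 0.6, log-odds 1.0 unless stated).
- Dropout of 10%, 25% or 30%: overstatement 0.32, 0.79 or 0.90.
- In-window Early Termination values for 25% of leavers, each set equal to the Week 6 change: overstatement falls to 0.20. At 50% and 75% it becomes understatement of 0.10 and 0.40. The repeated-measures estimate was not run with such values entered.
- Dropout driven by the unseen Week 12 value, over the same r and log-odds grid: t-test overstatement 0.46 to 1.35, repeated measures 0.16 to 1.10.
- 25%, 50% or 75% of leavers with no post-Baseline GAS, hence outside the FAS: repeated measures still overstates by 0.08, 0.25 or 0.38.
- Good responders leave instead: the t-test understates by 0.52.
- No Week 6 value, as for Q-LES-Q: bias of 0.09 SD falls only to 0.06 SD.

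**The case against.** The strongest reply rests on the Early Termination visit. A reader might infer that every early leaver is lost at Week 12. The documents do not support that: final assessments are due when drug is stopped, and the midpoint rule puts late ones into the Week 12 window, where the t-test uses them. This stands, and step 6 shows that it can shrink or reverse the bias. It does not help subjects who stop before the window opens.

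It can also be said that the Week 6 scores are not discarded, since they have their own summary and test. That is correct. The point is only that they do not inform the Week 12 estimate.

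The separate Handling Rules for Analysis Data, cited in Protocol 13.1.1 and SAP 7.2 but not reproduced, could hold a missing-data rule. So the absence of any such rule cannot be asserted. But Protocol 13.1 assigns analysis methodology to the SAP, and the SAP names the paired t-test.

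Finally, these are secondary endpoints without a power claim, and the assumed effect is large against its standard error. This limits the consequence to the size of the estimate and the coverage of its interval.

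**Conclusion.** The point holds as an improvement to the secondary analysis. The Week 12 paired t-test leaves out FAS subjects with no Week 12-window value and makes no use of their Week 6 score. If leaving depends on Week 6 response, the reported mean change is biased. With poor responders leaving, 16.7% dropout and no in-window Early Termination values, the assumed PHQ-9-like setting gives about 0.2 to 1.1 points on a 7-point change, that is 0.17 / 7 = 2% to 1.07 / 7 = 15%.

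Three stronger readings are tempting, and the documents do not support them:
- *Improvement will be overstated.* Nothing in the documents shows that the Week 6 score predicts dropout. Lack of effectiveness is one of seven withdrawal categories, and the direction depends on who leaves and when.
- *A repeated-measures model avoids the problem.* It removes the bias only if dropout depends on observed scores (missing at random). In the other settings tried it reduced the bias without removing it, and subjects with no post-Baseline GAS remain outside the FAS under either method.
- *The evidence of improvement is in doubt.* The bias is too small to reverse a test under any setting tried.

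**What to change.** In SAP 7.8.4:
- For GAS, PHQ-9, PDQ-D, WHO-5 and CGI-S, make the main analysis a likelihood-based repeated-measures model on the FAS. Use Baseline and all scheduled post-Baseline visits, visit as a factor and unstructured covariance. Report Week 6 and Week 12 mean change with 95% CI.
- State that Early Termination values enter through the SAP 7.1.2 windows, and whether the Week 9 call counts as a visit when the windows are set.
- Keep the paired t-test as the observed-case sensitivity analysis.
- Leave Q-LES-Q on the paired t-test, since it has no Week 6 value.

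Align the paired t-test wording in Protocol 2.0 (Secondary Effectiveness Analysis) and Protocol 13.1.3, or document the departure, for example in SAP 7.11.

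The cost is SAP wording, a few lines of SAS and the Protocol alignment, with no new data. The model relies on missing at random, and the reported improvement may come out slightly smaller.
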